C1) Hypothesized relationship. Increased $I_{\text{Electrode}}/E_{\text{brain}}$ is related to increased amplitude required for seizure titration (verification of non-human primate data depicted in 4A).

C2) Hypothesized relationship (Go-No-go). The ratio of fixed amplitude ECT (800 mA) relative to amplitude seizure titration will be associated with right hippocampal neuroplasticity.

interpretation, and alternatives: To illustrate the application of these principles, we use our preliminary data (4B3) and hypothesized relationships (4C1 and 4C2). We also use the example of 2% hippocampal growth as optimal for antidepressant response (optimal hippocampal growth will be determined with a receiver operating curve

(ROC) curve predicting Inventory of Depressive Symptomatology (IDS-C30) total score decrease during the R61). With traditional 800 mA amplitude, the 2% volume increase is related to an I/E_{brain} of ~ 625 mA/V/cm (**4B3**) and fixed/amplitude ratio of ~ 2.7 (**4C2**). Subject #1 (orange star) has a low (250 mA) seizure threshold (ST) (**4C1**), I/E_{brain} of ~ 600 mA/V/cm (**4C2**) and a fixed/amplitude ratio of $800/250 = 3.2$ (**4C2**). Subject #1 will need an input current of $2.7 \times ST = 2.7 \times 250$ mA = 675 mA for 2% hippocampal volume increase. In contrast, Subject #2 (green star) has a high (350 mA) seizure threshold, I/E_{brain} of ~ 750 mA/V/cm and a fixed/amplitude ratio of $800/350 = 2.3$. In order to achieve the 2% volumetric increase, Subject #2 will require an increased X/amplitude ratio from 2.3 to 2.7. Subject #2 will need an input current of $2.7 \times ST = 2.7 \times 350$ mA = 950 mA for 2% hippocampal volume increase. We stress that the fixed/amplitude ratio ~ 2.7 for 2% hippocampal volume increase is conceptual and will be determined during the R61.

H1: Amplitude seizure titration will have a positive correlation with I/E_{brain} (**Figure 4C1**). This is a replication of the data from the non-human primate data. The relationship between I/E_{brain} and amplitude titration is the foundation for the rationale of this proposal.

Statistical approach for H1: Let $(x, y)_i$ be the observed vector of response for I/E_{brain} and seizure threshold for each patient, $I = 1, \dots, n$. The Pearson correlation will be calculated and the standard one-sided t-test with 2 degrees-of-freedom will be conducted for testing whether the correlation is positive, $H_0: \rho > 0$.

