Power calculation for H1: The observed correlation in Figure 4A is $r = 0.84$ for non-human primates and we expect that the more conservative Cohen's "large" effect size $r = 0.5$ is a realistic lower bound for our population, thus a sample size of $n = 29$ provides 80% power at a $0.05 / 2 = 0.025$ significance level.

Go/No-Go criterion (H2): The ratio of amplitude titration to fixed amplitude ECT will demonstrate a linear relationship with treatment-responsive changes in hippocampal neuroplasticity. This relationship will determine the "neuroplasticity multiplier" to bridge from amplitude titration to hippocampal neuroplasticity.

Statistical approach for H2: We will perform a multiple regression accounting for covariates age and sex, $\%Vol_{Scaled} \text{ Change} = \beta_0 + \beta_1 M + \beta_2 \text{ age} + \beta_3 \text{ sex}$, where the effect size is $f^2 = R^2 / (1 - R^2)$, with R^2 the coefficient of determination with the interpretation of "the proportion of variance explained" in the response by the model over the grand mean. We will test whether the regression model explains a significant proportion of variance in the response, expecting that the key relationship is between $\%Vol_{Scaled}$ change and multiplier M .

Power calculation for H2: The relationship we are expecting in Figure 4C2 is derived from Figures 4B3 and 4C1. Starting with Figure 4B3, the relationship of I/E_{brain} on $\%Vol_{Scaled}$ change has a correlation of $r = -0.62$ with an effect size $f^2 = 0.624$, well above the Cohen's "large" effect size of $f^2 = 0.35$. Figure 4C1 is Figure A with the axes reversed, thus the correlation is $r = 0.84$. We will assume that the relationship between $\%Vol_{Scaled}$ Change and multiplier M will remain consistent with Cohen's "large" effect size. Then a sample size of $n = 36$ provides 80% power at a 0.05 significance level.

The Holm Procedure, a multi-step step-down procedure useful for endpoints with any degree of correlation, will adjust the two hypotheses below for multiple comparison³⁷. For our situation, this means H1 is tested at the 0.05 / 2 significance level and H2 is tested at $0.05 / (2-1) = 0.05$; however, H2 is tested only if H1 is significant.

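### The H2 power paragraph takes the threshold-to-I/Ebrain link at the primate r = 0.84, while the H1 paragraph plans the same link at r = 0.5; Go power should be stated over one common range

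*SAP*

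**What the plan says.** All of this is in SAP section 1 (Data Analysis), and the same text stands in Protocol section 13.

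- **H1 power.** The primate correlation between threshold and I/Ebrain is 0.84. For humans the plan discounts it: "effect size $r = 0.5$ is a realistic lower bound for our population". On that basis, "thus a sample size of $n = 29$ provides 80% power" at a 0.025 level, with "the standard one-sided t-test".
- **H2 power.** "The relationship we are expecting in Figure 4C2 is derived from Figures 4B3 and 4C1". The 4B3 link, I/Ebrain to hippocampal volume change, "has a correlation of $r = -0.62$ with an effect size $f^2 = 0.624". For the other link, "Figure 4C1 is Figure A with the axes reversed, thus the correlation is" r = 0.84. The plan then assumes that the effect of the multiplier M on volume change stays at Cohen's large value, f2 = 0.35, and gives n = 36 for 80% power at 0.05.
- **Decision rule.** Go requires rejecting β1 = 0 for M, adjusted for age and sex. H2 is tested only if H1 is significant.
- **Sample.** Protocol section 6 enrols 40 and expects 32 after 20% attrition. Protocol section 7 analyses after a minimum of 32.

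**The concern.** Figure 4C1 is the H1 relationship. In consecutive paragraphs the plan discounts it to 0.5 to size H1, then uses it undiscounted as one of the two links that support the H2 effect. The less cautious value therefore sits under the test that decides whether the programme continues.

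If the human link is nearer 0.5 than 0.84, the planned H2 effect could be well out of reach at 32 subjects even if the proposed mechanism is real. A reader of the plan sees only a single 80% figure and has no warning of this.

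**Working it through.** **Inputs.** From the SAP: 4B3 correlation 0.62 in absolute value; 4C1 link 0.84 (H2) or 0.5 (H1); f2 = 0.35; α = 0.05; three predictors (M, age, sex). From the protocol: 32 evaluable subjects.

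**Step 1: reproduce the plan's figures.** Power is taken from the noncentral F distribution with λ = f2 × n and n − 4 denominator degrees of freedom.
- H2, overall test (3 numerator df), f2 = 0.35: 79.6% at n = 35 and 81.0% at n = 36. The stated n = 36 reproduces.
- H2, β1 alone (1 numerator df), f2 = 0.35: 93% at n = 36 and 90% at n = 32. The stated 80% therefore belongs to the overall test and not to the Go test.
- H1, r = 0.5, one-sided 0.025, n = 29: 80.0% by Fisher's z and 81.3% by simulation. This also reproduces.

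**Step 2: join the two links.** Assumption A: threshold is related to volume change only through I/Ebrain, and M = 800/threshold is close to linear in threshold. Then |r(M, volume)| = link × 0.62 and f2 = r²/(1 − r²).
- Link 0.84: r = 0.84 × 0.62 = 0.521; r² = 0.271; f2 = 0.271/0.729 = 0.372, just above the planned 0.35.
- Link 0.5: r = 0.5 × 0.62 = 0.31; r² = 0.096; f2 = 0.0961/0.9039 = 0.106.
- Link needed for f2 = 0.35: √(0.35/1.35)/0.62 = 0.509/0.62 = 0.82.

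**Step 3: power of the β1 (Go) test under A**, with age and sex explaining no variance.

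| Link | f2 | n = 32 | n = 36 |
|---|---|---|---|
| 0.84 | 0.372 | 91% | 94% |
| 0.70 | 0.232 | 75% | 80% |
| 0.60 | 0.161 | 59% | 65% |
| 0.50 | 0.106 | 43% | 48% |

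Power of 80% needs a link of about 0.74 at n = 32, or 0.70 at n = 36.

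**Step 4: compare like with like at n = 36.** Moving from f2 = 0.35 to the 0.5 link takes the overall test from 81% to 31% and the β1 test from 93% to 48%.

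**Step 5: add the H1 gate.** In simulated trials with random predictors, H1 significance required and a link of 0.5, the probability of Go is about 37–38% at n = 32 and 43% at n = 36. A further simulation used M = 800/threshold directly, with an assumed threshold mean of 388 mA and SD of 60 mA; it gave about 37% at n = 32, so the nonlinearity of M matters little there.

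**The case against.** The case on the other side has four parts.

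- **The SAP never multiplies the two correlations.** It cites an observed f2 of 0.624, steps down to Cohen's large value and calls that an assumption, much as H1 does. This is fair, and it is why the point is not an arithmetic error. But the SAP names these two links as the source of the H2 effect, and their product at 0.84 lands almost exactly on the planned value, so the step down leaves almost no room for a weaker human link.
- **Correlations of 0.5 and 0.62 do not fix the correlation of M with volume.** Without assumption A it could lie anywhere in 0.31 ± √(0.75 × 0.6156), that is from −0.37 to 0.99. A partial correlation of about 0.29 between M and volume change given I/Ebrain would restore f2 = 0.35 at a link of 0.5; about 0.22 would give 80% β1 power at n = 32. This stands. The figures are conditional on A, although the SAP offers no other pathway.
- **0.5 is called a lower bound, not an expected value.** This also stands. At 0.60 the Go test has 59% power at n = 32.
- **Age and sex may explain some variance.** If they explain 10%, power at a 0.5 link and n = 32 rises only to about 47%.

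A reader might infer that true power is about 40% instead of 80%. The documents do not support this: it sets a gated one-df test at n = 32, at the lower bound, against an ungated three-df test at n = 36. A reader might also infer that 80% power requires nearly the primate correlation. That is true of f2 = 0.35, but the Go test reaches 80% at 0.70 to 0.74. Nor do the documents say how a No-Go would be interpreted, so a misreading cannot be presumed.

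**Conclusion.** The inconsistency is real: the same link is planned at 0.5 for H1 and taken at 0.84 in deriving the H2 effect. The calculation from f2 = 0.35 to n = 36 is correct; the support for f2 = 0.35 is what does not match the H1 paragraph.

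The size of the problem depends on full mediation through I/Ebrain, on M being near-linear in threshold, and on 0.62 holding in the new sample. Under those conditions, the chance of Go is comfortable if the human link is above about 0.74 and falls below one half at the plan's own lower bound. A single 80% figure, attached to a different test and to 36 subjects, does not convey that range. The point should be corrected because the Go/No-Go decision relies on it, but it does not show that the trial is underpowered at the link the investigators expect.

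**What to change.** In the H2 power paragraph of the SAP, and in Protocol section 13:

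1. Use the same range for the 4C1 link, 0.5 to 0.84, in both power calculations.
2. Write out the chain from 4B3 and 4C1 to f2, and state that it assumes threshold relates to volume change only through I/Ebrain.
3. Replace the single 80% figure with power of the β1 test at 32 evaluable subjects over that range: about 43% at 0.5, 59% at 0.6, 75% at 0.7 and 91% at 0.84. Give the probability with the H1 gate alongside (37–38% at 0.5).
4. Add that a No-Go is not strong evidence against the mechanism if the observed link is near 0.5.

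The cost is a less favourable stated power and a change of wording. Enrolment, procedures, the model and the Go rule stay as they are.

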## **6. Study Timelines**

Our total sample size (n = 40) allows for a conservative 20% attrition rate leaving a final sample size of 32. This recruitment rate of 20 subjects per year will complete subject recruitment 2 years after study initiation. We have a successful recruitment and retention history for ECT-imaging investigations of approximately 20 subjects per year with this demographic for the last decade and are well poised to meet the recruitment/enrollment goals delineated in this project proposal.

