## **7. Study Endpoints**

After recruiting a minimum of 32 subjects, we will assess the following relationships: 1) amplitude-determined seizure threshold and whole brain conductivity metrics ( $I/E_{brain}$ ); and 2) amplitude titration and changes in right hippocampal volume with 800 mA ECT.

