Go/No-Go criterion (H2): The ratio of amplitude titration to fixed amplitude ECT will demonstrate a linear relationship with treatment-responsive changes in hippocampal neuroplasticity. This relationship will determine the "neuroplasticity multiplier" to bridge from amplitude titration to hippocampal neuroplasticity.

Statistical approach for H2: We will perform a multiple regression accounting for covariates age and sex,  $\%Vol_{Scaled}$  Change =  $\beta_0 + \beta_1 M + \beta_2$  age +  $\beta_3$  sex, where the effect size is  $f^2 = R^2 / (1 - R^2)$ , with  $R^2$  the coefficient of determination with the interpretation of "the proportion of variance explained" in the response by the model over the grand mean. We will test whether the regression model explains a significant proportion of variance in the response, expecting that the key relationship is between  $\%Vol_{Scaled}$  change and multiplier  $M$ .

Power calculation for H2: The relationship we are expecting in Figure 4C2 is derived from Figures 4B3 and 4C1. Starting with Figure 4B3, the relationship of  $I/E_{brain}$  on  $\%Vol_{Scaled}$  change has a correlation of  $r = -0.62$  with an effect size  $f^2 = 0.624$ , well above the Cohen's "large" effect size of  $f^2 = 0.35$ . Figure 4C1 is Figure A with the axes reversed, thus the

correlation is  $r = 0.84$ . We will assume that the relationship between %VolScaled Change and multiplier M will remain consistent with Cohen's "large" effect size. Then a sample size of  $n = 36$  provides 80% power at a 0.05 significance level.

The Holm Procedure, a multi-step step-down procedure useful for endpoints with any degree of correlation, will adjust the two hypotheses below for multiple comparison. For our situation, this means H1 is tested at the  $0.05 / 2$  significance level and H2 is tested at  $0.05 / (2-1) = 0.05$ ; however, H2 is tested only if H1 is significant.

The Go/No-Go criterion is set to "Go" if we can reject the null hypothesis that  $H_0: \beta_1=0$  at a 0.05 significance level in the model specified in Hypothesis H2, that is, that multiplier M remains a significant predictor of %VolScaled Change after adjusting for age and sex.

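### The H2 sample size of 36 fits the whole-model F test, not the β1 test that decides Go, and exceeds the 32 subjects the protocol expects to keep

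*SAP*

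**What the plan says.** The SAP, under Power calculation for H2, assumes Cohen's large effect (f² = 0.35) and concludes: "Then a sample size of $n = 36$ provides 80% power at a 0.05 significance level". Protocol Section 13 carries the same text ("provides 80% power at a 0.05 significance level").

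Under Statistical approach for H2, the SAP regresses scaled hippocampal volume change on M, age and sex. It defines f² = R²/(1 − R²), with R² the variance explained "in the response by the model over the grand mean", and describes the test this way: "We will test whether the regression model explains a significant proportion of variance in the response". The power paragraph then attaches the large effect to one predictor, assuming that the relation between volume "Change and multiplier M will remain consistent with" Cohen's large value.

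The Go/No-Go paragraph that closes the SAP uses a different test: Go requires rejecting β1 = 0 at 0.05 after adjustment for age and sex. The Holm paragraph adds a condition: "however, H2 is tested only if H1 is significant".

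On sample size, Protocol Section 6 says that enrolling 40 "allows for a conservative 20% attrition rate leaving a final sample size of 32". Section 7 says: "After recruiting a minimum of 32 subjects, we will assess the following relationships".

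**The concern.** A power statement should describe the test that decides the question, at the number of subjects the plan expects to analyse. Here the stated size of 36 is larger than the planned final 32, and the test it appears to describe is not the one that decides Go. The two tests can disagree: the model can be significant through age or sex while β1 is not, and β1 can be significant while the 3-df test is not.

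H2 is the sole Go/No-Go criterion. Anyone weighing a No-Go needs to know how likely Go was under the assumed effect, and the plan does not supply that figure. Nor does it fix what f² = 0.35 refers to, and that choice decides which side of 80% the Go test falls on.

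**Working it through.** **Inputs.** α = 0.05, f² = 0.35, three predictors, stated n = 36 (SAP, H2 paragraphs). 40 enrolled, 20% attrition, 32 remaining (Protocol Section 6). H1: r = 0.5 as the lower bound, r = 0.84 observed in primates, α = 0.025 one-sided (SAP, H1 and Holm paragraphs).

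**Formula.** Noncentral F with u numerator df, n − 4 denominator df and noncentrality λ = f²·n. The whole-model test has u = 3; the test of β1 has u = 1.

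**1. Reproducing the plan's figure.** At f² = 0.35:

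| n | whole model (u = 3) | β1 (u = 1) |
|---|---|---|
| 24 | – | 0.787 |
| 25 | – | 0.805 |
| 32 | 0.749 | 0.898 |
| 34 | 0.781 | – |
| 35 | 0.796 | – |
| 36 | 0.810 | 0.931 |

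The smallest n with 80% power for the whole-model test is 36, as stated. For β1 it is 25. The SAP does not name the test behind 36. That it is the whole-model test is inferred from the definition of f², the sentence describing the test, and this match.

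**2. Sample.** 40 × 0.8 = 32. Keeping 36 of 40 allows attrition of only 1 − 36/40 = 10%. At 20% attrition, 36 analysed would need 36/0.8 = 45 enrolled. At 32 the whole-model power is 75%.

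**3. β1 at n = 32, by meaning of f².**
- *Partial effect of M is 0.35:* power is 0.898.
- *Whole-model f² is 0.35:* R² = 0.35/1.35 = 0.259. If M carries a share s of that R², its partial f² is 0.35s. Power of 80% at n = 32 needs a partial f² of 0.263, so s = 0.263/0.35 = 0.75. Power is below 80% once age and sex carry more than about 25% of R². The documents give no shares, so any value of s is an assumption.

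**4. Random predictors.** M and age are observed, not set by design. The simulation used normal M and age, balanced sex and at least 100,000 runs. Whole-model power is about 71% at 32, 75% at 34 and 78% at 36. β1 power at partial f² = 0.35 is about 84% at 32 and reaches 80% at n = 29. On the whole-model meaning, the β1 threshold is a share of about 0.88 for M, which is about 12% for age and sex.

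**5. The H1 gate at n = 32.** At r = 0.5, H1 power is 0.854. With β1 power of 0.845, the probability of passing both lies between 0.854 + 0.845 − 1 = 0.699 and 0.845, whatever the dependence. If volume change relates to I/E_brain only through M (an assumption made here), simulation gives about 72%. At r = 0.84 H1 is almost certain to pass, and the joint figure is about 84–85%.

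**The case against.** The strongest reply is that no harm to the deciding test is shown. The wording of the power paragraph favours reading 0.35 as M's own effect. The inputs it cites, r = −0.62 and r = 0.84, are bivariate and contain no contribution from age or sex. Their product, which the plan does not itself compute, is 0.52, giving f² = 0.37, close to 0.35. On that reading β1 has 84–90% power at 32, the whole-model 75% is a floor, and sizing on the 3-df test was the more demanding choice. The protocol also calls its 20% attrition conservative and 32 a minimum, so 36 lies within the expected range of 32 to 40. The H1 condition is already stated.

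Much of this stands. It rules out a claim that the Go decision is underpowered, and the gate costs almost nothing if r is near 0.84. It does not repair the mismatch. The SAP's only formal definition of f² is the whole-model one, and 36 follows only if 0.35 is used that way. The protocol names 32 as its final sample. Stating that H2 is conditional on H1 is not the same as saying what that does to the chance of Go.

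**Conclusion.** The concern holds. The arithmetic behind 36 is correct for the whole-model test, but the stated power describes neither the planned final sample nor the deciding test. At 32 the whole-model power is about 75% (71% with random predictors), roughly 5 points below the stated 80%. β1 power at 32 is about 90% (84%) if 0.35 is M's partial effect. It falls below 80% only if 0.35 is the whole-model effect and age and sex carry more than about 25% (12%) of R². At H1's own lower bound, the chance of passing both tests is 70–84%, taking β1 power as 84%. This is a reporting fault in the figure behind the sole Go/No-Go criterion. It should be corrected, but it is not evidence that the trial is too small.

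**What to change.** Make these changes in the SAP's H2 paragraphs and in the same text of Protocol Section 13:

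1. State whether f² = 0.35 is M's partial effect given age and sex, or the whole-model effect. If whole-model, give the assumed share of R² for M and the power that follows.
2. Replace the n = 36 sentence with the power of the β1 test at the planned final sample. If the partial meaning is chosen, for example: *With 32 evaluable subjects (40 enrolled, 20% attrition) and a partial f² of 0.35 for M given age and sex, the two-sided test of β1 = 0 at 0.05 has about 90% power (about 84% with random predictors).* Section 7 speaks of recruiting a minimum of 32, so make clear that 32 means subjects analysed for H2.
3. In Statistical approach for H2, name β1 = 0 as the H2 test and label the whole-model F test descriptive.
4. Add one sentence saying that, because H2 is tested only if H1 is significant, the chance of Go is lower than the H2 power.

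The cost is wording only. Enrolment, α, the Go rule and the timing of analysis do not change. The whole-model figure becomes less favourable (75% at 32), and the team must commit to one meaning of f². If it chooses the whole-model meaning, the stated β1 power may be below 80%.

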Amplitude titration, as proposed here, can reduce the variability related to fixed amplitude dosing and optimize clinical and cognitive outcomes. *The goal of this project is to change standard ECT parameter selection from a fixed amplitude with variable pulse number (combination of pulse train duration and frequency) to an individualized and empirically determined amplitude with fixed pulse number.* To achieve this goal, we will focus on the relationship between amplitude titrated seizure threshold and treatment-responsive changes in hippocampal neuroplasticity with RUL fixed amplitude ECT. Fixed amplitude ECT results in variable E-fields and inconsistent changes in hippocampal neuroplasticity. In contrast, computational and pre-translational investigations have demonstrated that amplitude titration results in consistent E-fields. Seizure titration amplitudes (based on historic data, 233 to 544 mA) are below the amplitude range of FDA-approved ECT devices (500 to 900 mA) and will require an adaptor to reduce the amplitude (FDA Investigational Device Exemption). Amplitude titration will also be below the hippocampal neuroplasticity threshold and insufficient for antidepressant response. The difference between RUL amplitude titration and RUL fixed amplitude (800 mA) ECT will determine the degree of target engagement with the hippocampus. To illustrate, subjects with low amplitude seizure threshold of ~250 mA (800/250, high fixed/titration amplitude ratio) will have significant changes in hippocampal neuroplasticity. Subjects with high amplitude ~500 mA (800/500, low fixed/titration ratio) will have minimal changes in hippocampal neuroplasticity. The relationship between amplitude titration and fixed amplitude hippocampal neuroplasticity will be used to develop the amplitude multiplier required for consistent and clinically effective ECT dosing. Amplitude titration with

multiplier will be associated with the “sweet spot” for hippocampal neuroplasticity: sufficient for antidepressant response but not excessive thus resulting in cognitive safety.

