Older depressed subjects (n = 40) will first receive RUL amplitude titration (first treatment) and then RUL fixed amplitude (800 mA) and fixed pulse number ECT (subsequent treatments). We will 1) verify results from pre-translational investigations that demonstrated the relationship between current pulse amplitude and a whole brain E-field metric ( $I/E_{brain}$ ), and 2) determine the relationship between current pulse amplitude and treatment-responsive changes in hippocampal neuroplasticity from RUL fixed-amplitude (800 mA) ECT.

H1: Amplitude seizure titration will have a positive correlation with  $I/E_{brain}$ .

H2, Go/No-Go criterion: The ratio of amplitude titrated seizure threshold to fixed amplitude ECT will demonstrate a linear relationship with treatment-responsive changes in hippocampal neuroplasticity. This relationship will determine the “neuroplasticity multiplier” to bridge from amplitude titration to hippocampal neuroplasticity.

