the degree of target engagement with the hippocampus. To illustrate, subjects with low amplitude titration of ~250 mA (800/250, high fixed/titration amplitude ratio) will have significant changes in hippocampal neuroplasticity. Subjects with high amplitude titration ~500 mA (800/500, low fixed/titration ratio) will have minimal changes in hippocampal neuroplasticity. The relationship between amplitude titration and fixed amplitude hippocampal neuroplasticity will be used to develop the amplitude multiplier required for consistent and clinically effective ECT dosing. A randomized controlled trial will then compare hippocampal neuroplasticity, antidepressant, and cognitive outcomes between amplitude titration with neuroplasticity multiplier (fixed pulse number) and traditional fixed amplitude ECT (800 mA, variable pulse number) in older depressed subjects.

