The Go/No-Go criterion is set to "Go" if we can reject the null hypothesis that $H_0: \beta_1=0$ at a 0.05 significance level in the model specified in Hypothesis H2, that is, that multiplier M remains a significant predictor of $\%Vol_{Scaled}$ Change after adjusting for age and sex.

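### The Go rule names no sign for β1, and H2 states the ratio behind multiplier M the opposite way round from Figure 4C2 and every worked example

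*SAP*

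**What the plan says.** The H2 model regresses scaled percentage volume change on M, age and sex (Protocol section 13; SAP section 1). M is called a multiplier, and no formula stands beside the model.

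- **Go rule.** In the SAP, Go needs rejection of β1 = 0 "at a 0.05 significance level in the model specified in Hypothesis H2, that is, that multiplier M remains a significant predictor of" volume change. The Protocol has the same rule, glossed as meaning "that multiplier M remains a significant predictor of %VolScaled Change after adjusting for age and sex". Neither document states a sign. The preceding paragraph adds that H2 is tested only if H1 is significant.
- **H2, Protocol section 1.** "The ratio of amplitude titrated seizure threshold to fixed amplitude ECT will demonstrate a linear relationship" with hippocampal change: threshold over fixed.
- **H2, SAP section 1** (and Protocol section 13). "The ratio of amplitude titration to fixed amplitude ECT will demonstrate a linear relationship with treatment-responsive changes in hippocampal neuroplasticity": again threshold over fixed, and again linear.
- **Figure 4 legend, C2**, labelled as the Go/No-Go relationship. "The ratio of fixed amplitude ECT (800 mA) relative to amplitude seizure titration will be associated with right hippocampal neuroplasticity": fixed over threshold.
- **Worked subjects.** 800/250 = 3.2 and 800/350 = 2.3: fixed over threshold.
- **Predicted direction.** Protocol section 2 says subjects with a low threshold ("800/250, high fixed/titration amplitude ratio) will have significant changes in hippocampal neuroplasticity"). Protocol section 1 says those with a high threshold ("800/500, low fixed/titration ratio) will have minimal changes in hippocampal neuroplasticity").

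H1, by contrast, names a positive direction and a one-sided test.

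**The concern.** Go/No-Go is the main decision of this phase, and the same regression is meant to supply the neuroplasticity multiplier. Two gaps meet here. First, the rule accepts a significant slope in either direction, although only one direction supports the rationale. Second, which direction that is depends on how M is oriented: the predicted β1 is positive for fixed/threshold and negative for threshold/fixed. Until M is fixed, a sign clause cannot even be written, so the two need one joint repair.

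The orientation also matters beyond the sign. H2 claims linearity, and volume cannot be linear in a ratio and in its reciprocal at once. Two analysts following different sentences would fit different models, obtain different p-values and read off different multipliers.

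**Working it through.** 1. **The plan's own figures.** From r = −0.62, f² = 0.3844/0.6156 = 0.624, as stated. For n = 36, I used a noncentral F with f² = 0.35, α = 0.05, λ = 0.35n and n − 4 denominator df. The whole-model test (3 numerator df) first reaches 80% at n = 36, with power 0.810. The test of β1 alone (1 df, partial f² = 0.35) first reaches it at n = 25. So 36 reproduces, but for the whole-model test described in the H2 approach, not for the β1 test in the Go rule. At the 32 completers expected in Protocol section 6, power is 0.749 for the whole model and 0.898 for β1.

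2. **The two ratios.** Over the historic 233–544 mA range (Protocol section 1), threshold/800 runs from 233/800 = 0.29 to 544/800 = 0.68, and 800/threshold from 3.43 down to 1.47. Taking thresholds as uniform over that range (an assumption), their correlation is −0.976.

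3. **Shape.** Use the Protocol's example thresholds of 250 and 500 mA and give both lines the same volumes at those ends. At 350 mA the fitted effect, as a share of the way from the 500 mA value to the 250 mA value, is:
   - linear in 800/threshold: (2.286 − 1.6)/(3.2 − 1.6) = 0.43
   - linear in threshold/800: (500 − 350)/(500 − 250) = 0.60

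4. **Multiplier.** This illustrates the analysis only. With the same two ends, the half-way effect falls at a fixed/threshold ratio of (1.6 + 3.2)/2 = 2.40 on one scale and at 1/((0.3125 + 0.625)/2) = 2.13 on the other. The plan's conceptual 2.7 lies (2.7 − 1.6)/1.6 = 0.6875 of the way up. On the reciprocal scale that point is 0.625 − 0.6875 × 0.3125 = 0.410, a ratio of 1/0.410 = 2.44. If the two worked subjects (250 and 350 mA) are the ends, the pair is 2.70 and about 2.63.

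5. **Go decision.** Simulation with n = 32, f² = 0.35 carried by M, thresholds uniform over 233–544 mA, age and sex as noise covariates, H1 one-sided at 0.025 and β1 two-sided at 0.05. The two orientations give different gated decisions in about 4–5% of trials, and in about 6–7% at f² = 0.20. Across other assumed threshold spreads (250–550 mA, lognormal, with and without 50 mA steps) the range is 3–7% at f² = 0.35. With H2 tested alone on a 50 mA grid from 250 to 550 mA, and fixed/threshold true, power is 0.856 for that orientation and 0.835 for its reciprocal, with 4.9% of decisions differing.

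6. **Sign.** At planning values there were no wrong-sign Gos in 40,000 trials. If H2 is null, a two-sided 5% test puts 2.5 points in each tail. After the H1 gate, wrong-sign Go is about 1–2.7%, depending on how strongly H1 holds (r = 0.5 to 0.84) and on how I/E_brain relates to volume. Requiring a positive estimate at r = 0.84 takes false Go from about 5% to about 2.5%.

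**The case against.** The strongest reply is that M can be recovered. The H2 power paragraph says the expected relationship is the one in Figure 4C2 and then describes it as volume change against M. The legend gives that predictor as fixed over threshold, and the examples multiply a threshold by 2.7 to obtain a current, which works only for that orientation. The figure itself is not reproduced, so an axis label may also settle it. This stands: M is not unknowable. What remains is that the formal hypothesis says the reverse in all three places, and a prespecified decision rule should not rest on inference.

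On sign, it is fair to say that nobody would act on a wrong-direction slope, that it does not arise at planning values, and that the nominal 5% is not exceeded. But then stating the sign loses nothing.

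Four stronger readings are tempting, and the documents do not support them:
- *Protocol section 7 offers a further definition of M.* Its "amplitude titration and changes in right hippocampal volume with 800 mA ECT" is a one-line summary that specifies no regressor.
- *The H2 test is inflated to about 6%.* That needs the orientation to be picked after seeing the data, which nothing suggests. Even then, gated false Go is about 5.1–6.2%.
- *The multiplier would shift by the gaps in step 4.* Those force equal volumes at both ends, which least squares does not. Simulated fits gave median differences of 0.06–0.13, and these are indicative only because the target volume is still to be estimated.
- *The Holm paragraph is an error in testing.* The procedure described is a fixed sequence that is valid and conservative. Only the name is off.

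**Conclusion.** The wording conflict and the missing sign are plain in both documents and depend on no assumption. Fixed/threshold is the likely intent. The consequences for the decision are modest because the two ratios are so highly correlated: about 4–5% of Go decisions change at n = 32 and f² = 0.35, and a wrong-sign Go is a 1–2.7% event confined in practice to a null H2. Those percentages rest on the assumed threshold distribution and on M carrying the whole effect. The firmer consequences are qualitative: the predicted sign reverses, the linearity claim means something different, and the multiplier read from the fit changes. It should be corrected before analysis, but it does not undermine the design, and it is not a claim that the sample size of 36 is wrong.

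**What to change.** - Beside the model in Protocol section 13 and SAP section 1, write: M = 800 mA / amplitude-titrated seizure threshold. Reword H2 in Protocol sections 1 and 13 and in the SAP to the same orientation.
- State one rule: Go if H1 is rejected, β1 = 0 is rejected at two-sided 0.05, and the estimated β1 is greater than 0.
- Say that this β1 test is the decision test, and that the sentence on whether the regression model as a whole is significant is not.
- Optional, wording only: call the H1-then-H2 gate a fixed sequence instead of Holm. The gate itself need not change.

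The cost is a few words and no data. The sign clause costs no probability of Go at planning values and roughly halves false Go when H1 holds strongly. Fixing the orientation costs about 2 points of power if the other form is the true one (0.856 against 0.835 in the mirror case above). This concerns the analysis variable only; no multiplier value or dose is proposed.
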